8.2.4 Patient/Subject Data Listings

Data collected in the electronic case report form (eCRF) will generally be listed. eCRF check questions (e.g., reminders) will not be listed.

Listings will be sorted by treatment group, study center, patient/subject id, visit and assessment time as applicable. If center id is part of patient/subject id, then center could be omitted.

In CRF modules where a date is recorded, the relative day may be included in the corresponding listing. In modules where both a start date and stop date are recorded, the duration may be included in the listing.

8.2.5 Subject Disposition

The numbers of subjects screened, enrolled, completed, discontinued, and withdrawn during the study, as well as the reasons for all post-enrolment discontinuations will be listed and/or summarized by treatment group. Disposition and reason for study discontinuation will also be provided as a by-subject listing.

8.2.6 Demographic and Other Baseline Characteristics

Demographics and baseline characteristics will be summarized by treatment group using appropriate descriptive statistics.

The following summaries will be given by treatment and in total:

- Demography
 - Age (years)
 - Age (years), categories (55 to <65, 65 to <75, 75 to <85)
 - Sex (Male or Female)
 - Race (White, Asian, Black or African American, American Indian or Alaska Native, Native Hawaiian or Other Pacific Islander, Other)
 - Ethnicity (Hispanic or Latino, Not Hispanic or Latino, Not Reported, Unknown)
 - Height (cm)
 - Weight (kg)
 - BMI (kg/m²)

8.2.7 Primary Analysis

The co-primary endpoints in this clinical trial are the change from baseline to Week 12 in ADAS-Cog11 score and the ADCS-CGIC score at Week 12 between buntanetap-treatment (pooling three treatment arms together) and placebo.

The statistical hypothesis to be tested for co-primary endpoint ADAS-Cog11 score is described as:

• Null Hypothesis (H0):

The difference in change in ADAS-Cog11 score from baseline to Week 12 between buntanetap-treatment (pooling three treatment arms together) and placebo = 0.

Alternative Hypothesis (H1):

The difference in change in ADAS-Cog11 score from baseline to Week 12 between buntanetap-treatment (pooling three treatment arms together) and placebo $\neq 0$.

The statistical hypothesis to be tested for co-primary endpoint ADCS-CGIC score is described as:

Null Hypothesis (H0):

The difference in ADCS-CGIC score at Week 12 between buntanetap-treatment (pooling three treatment arms together) and placebo = 0.

Alternative Hypothesis (H1):

The difference in ADCS-CGIC score at Week 12 between buntanetap-treatment (pooling three treatment arms together) and placebo $\neq 0$.

The two co-primary endpoints will be analyzed via MMRM. The model for the co-primary endpoint ADAS-Cog11 score will include treatment, timepoint, treatment-by-timepoint interaction as the fixed effects and baseline as the covariate. The Model for the co-primary endpoint ADCS-CGIC score will include treatment, timepoint, treatment-by-timepoint interaction as the fixed effects. The variance-covariance matrix will be assumed to be UN.

This analysis will be conducted after all participants have reached Week 12 or early withdrawal, whichever comes first. The primary analysis will be conducted in ITT. The mITT and PPS will be used to support the primary analysis.

Descriptive statistics per visit and change from baseline for each visit will be provided.

As the study is also designed to explore the effectiveness of three buntanetap-treatment dose levels on co-primary endpoints, similar MMRM will be applied comparing each buntanetap-treatment dose arm with placebo.

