# 6.8 Analysis of Primary Endpoints

The co-primary endpoints are the change from baseline to 12 weeks in ADAS-Cog11 scores and the ADCS-CGIC scores at 12 weeks. The ADAS-Cog11 will be analyzed via mixed models for repeated measures (MMRM). The model for ADAS-Cog11 will include treatment, timepoint, treatment-by-timepoint interaction as the fixed effects, baseline ADAS-Cog11as the covariate, and subjects as random effect. The Model for ADCS-CGIC will include treatment, timepoint, treatment-by-timepoint interaction as the fixed effects, and subjects as random effect. An unstructured covariance matrix will be used and the Kenward-Roger approximation will be used to adjust the denominator degrees of freedom. The change from baseline and the differences in the change from baseline between treatments will be based on the Least Square Means from this model. The two-sided 95% confidence intervals of the treatment differences will be presented.

Ver. 3.1; 09-25-2023

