# 6.10.1 Re-estimation of Sample Size

The initial planned sample size was determined for ADAS-Cog11 based on a targeted power of 90% to detect a delta of 2.7 between the treatment (pooling three arms together) and placebo, with a common standard deviation of 6.0 at a two-sided significance level alpha of 5%. This sample size will also have a power of 89% to detect a significant difference for the co-primary effectiveness variable ADCS-CGIC at a two-sided significance level of 5%, assuming a delta of 0.22 with a common standard deviation of 0.5. Accounting for an expected drop-out rate of 12.5%, a sample size of approximately 320 participants (80 per treatment arm) was calculated to achieve 280 evaluable participants (70 per treatment arm).

To guarantee sufficient power for the primary trial objectives, sample size will be re-estimated based on the calculated conditional power at the interim analyses. The conditional power for each co-primary endpoint will be calculated at the significance level of 0.05 separately, according to the methodology and equation from Mehta and Pocock (2011). The sample size will only be increased if the conditional powers for both co-primary endpoints are >50% (and <90%), otherwise, the trial will continue as planned, i.e., no decrease in sample size or stopping the trial early for futility or efficacy success at the interim analysis. The target power is 90% and maximum sample size per group is set to be 100 participants per arm. Specifically, if both conditional powers at interim analysis are >50%, then each arm will be increased to 100 participants. Otherwise, the trial will continue as is.

Chen, Lan and Demets (2004) have shown that, when conditional power  $\geq 50\%$ , one may increase sample size to n2\* and the conventional test statistics and critical values can be used at the final analysis, the overall type I error rate will not be inflated. Further, Chen, Yuan and Li (2018) demonstrated that the conventional maximum likelihood estimate, and coverage error of its conventional confidence interval are generally small following sample size adjustment. Therefore, conventional point estimate and confidence interval are recommended to be used when applying the 50% conditional power principle for sample size re-estimation, to keep consistent statistics in both hypothesis test and statistical inference.

Confidential Page 29 of 57

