- The Intent-to-Treat set (ITT) will consist of all participants who are randomized. The primary
 efficacy analyses will be based on the ITT.
- The Modified Intent-to-Treat set (mITT) will consist of all participants who are randomized, receive at least one dose of study drug, and have both a baseline and at least one postbaseline assessment value for the ADAS-Cog11 or ADCS-CGIC score after taking study drug. The mITT will be used to support the primary efficacy analyses.
- The Safety analysis set (SAF) will consist of all randomized participants who receive at least one dose of study drug. The safety analyses will be based on the SAF.

- The Per-protocol set (PPS) will consist of all participants in the mITT who complete at least 67 days treatment exposure (Last dose date - First dose date + 1 >= 67 days) without any major protocol deviations that potentially could impact the primary efficacy endpoint. The membership of this analysis set will be determined prior to database lock. The PPS will be used to support the primary and secondary endpoints as supportive analyses.
- The PK set will analyze all available data from safety participants receiving buntanetap and with at least one sampling profile allowing derivation of at least one PK parameter.

Protocol deviations leading to exclusions from PPS include but are not limited to the following:

- Non-fulfilment of all inclusion criteria
- Fulfilment of at least one exclusion criterion
- Use of certain concomitant medications (for details see section 8.3.11)

The final criteria for the PPS, regarding which protocol deviations that warrant exclusion, will be determined before breaking the blind.

Baseline presentations will be based on the SAF.

Safety presentations will be based on the SAF.

Exposure to study drug will be given for the SAF.

The ITT and mITT will be analyzed according to randomized (planned) treatment. Safety and PPS will be analyzed on actual treatment.

Plasma concentration-time data for buntanetap will be based on the SAF. PK parameters derivations and statistical analyses are described in a separate PK SAP and will be based on the PK set (see Section 8.5).

8 Statistical and Analytical Plans

8.1 **Changes to the Planned Analyses**

There have been no changes in the planned analyses in the study protocol.

8.2 **Hypothesis and Statistical Methods**

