8.2.3 Summary Statistics

Data will be summarized by means of summary statistics. Summary statistics will be provided for the variables described in the following sections.

Categorical data will be presented as counts and percentages, i.e., n (xx.x%). Percentages will be based on the number of subjects in the analysis data set used and given as integers. Zero frequencies will be given without percentages.

For continuous variables, these statistics will include the number of subjects, mean, SD, median, minimum, and maximum.

All variables will be analyzed descriptively with appropriate statistical methods: categorical variables by frequency tables (absolute and relative frequencies) and continuous variables by sample statistics (i.e., number of observations, mean, SD, 95% CI of the mean, minimum, median, first and third quartiles and maximum). Minimum and maximum values will be displayed as reported.

Since the two co-primary endpoints and secondary endpoints are captured at multiple visits, the method selected to analyze the endpoints, which are treated as continuous, will be a Mixed Model for Repeated Measures (MMRM). For the co-primary endpoint ADAS-Cog11 score and secondary endpoints, MMRM will be applied with change from Baseline score as the response (dependent variable) and with Baseline value as a covariate and treatment, timepoint, treatment-by-timepoint interaction as fixed effects (independent variables). The Model for co-primary endpoint ADCS-CGIC score will include treatment, timepoint, treatment-by-timepoint interaction as the fixed effects. Estimation of parameters will be done by means of Restricted Maximum Likelihood method. The Unstructured (UN) variance-covariance structure will be initially used to explore the variance-covariance matrix across visits. If the algorithm doesn't converge, a heterogeneous Toeplitz (TOEPH) as the covariance matrix will be tried first, and then first-order autoregressive (AR(1)) to achieve convergence. The Kenward-Roger approximation will be used to estimate denominator degrees of freedom. The two-sided 95% CI of the treatment differences will be presented.

The co-primary endpoint ADAS-Cog11 score and secondary endpoints will be analyzed using the model explained above as follows:

```
<Endpoint>= intercept + Base + T + V + T*V,
```

with

Base: baseline score;

T: treatment;

V: post-baseline visit (Week 6, Week 12).

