8.6 Adjustment for Covariates

Baseline value will be used as a covariate in the MMRM analyses for the co-primary endpoint ADAS-Cog11 score (see Section 8.3.7).

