The MMRM analysis of the two co-primary endpoints assumes that data are missing at random (MAR). The analysis will be conducted in ITT set and subjects will be analyzed as randomized. ITT subjects discontinue from the study for any reason without completing the study are considered intercurrent events. To assess the robustness of this MAR assumption, a conservative control-based multiple imputation method based on missing not at random (MNAR) assumption will be applied to impute missing data arising from intercurrent events for the two co-primary endpoints analyses. In this MNAR approach, subjects who do not complete the study, missing data will be imputed by observed data obtained from the placebo group using multiple imputation with Markov Chain Monte Carlo (MCMC) simulation method for each treatment separately. For the co-primary endpoint ADAS-Cog11 score, the variables for the imputation model will include ADAS-Cog11 score at baseline, Week 6, and Week 12. The ROUND, MINIMUM and MAXIMUM options will be utilized to ensure imputed values are clinically plausible integers (0 - 70). For the co-primary endpoint ADCS-CGIC score, the variables for the imputation model will include ADCS-CGIC score at Week 6 and Week 12. The ROUND, MINIMUM and MAXIMUM options will be utilized to ensure imputed values are clinically plausible integers (1 -7). Approximately 50 datasets will be imputed and the same MMRM analysis as the one applied to the primary analysis will be fitted. The results from these 50 analyses will be combined using Rubin's rule to construct the treatment estimates from the parameter estimates and associated standard errors. The difference of the treatment means (active minus placebo) will be presented with the associated standard error and two-sided 95% confidence interval. The imputation will be performed for the two co-primary endpoints separately. Two random seed numbers will be selected for the multiple imputation procedure and will be retained.

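### The ADCS-CGIC co-primary model uses no baseline covariate, although baseline ADAS-Cog11 is scheduled for every participant; the cost is some precision, not validity (minor).

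*SAP*

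**What the plan says.** Protocol 6.8 and the SAP specify the same ADCS-CGIC model. Protocol 6.8: "The Model for ADCS-CGIC will include treatment, timepoint, treatment-by-timepoint interaction as the fixed effects, and subjects as random effect". SAP 8.2.7: "The Model for the co-primary endpoint ADCS-CGIC score will include treatment, timepoint, treatment-by-timepoint interaction as the fixed effects". The model equation in SAP 8.2.3 likewise has no baseline term for this endpoint.

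For ADAS-Cog11 and the secondary endpoints, SAP 8.2.3 models change from baseline "and with Baseline value as a covariate and treatment, timepoint, treatment-by-timepoint interaction as fixed effects". SAP 8.2.8 repeats this for ADCS-ADL, MMSE and DSST. SAP 8.6, the section on covariates, mentions only one endpoint: "Baseline value will be used as a covariate in the MMRM analyses for the co-primary endpoint ADAS-Cog11 score".

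In the Schedule of Events (Appendix 1 of both documents), ADAS-Cog11 and MMSE are marked at the Baseline visit. ADCS-CGIC is evaluated there but not scored (footnote d). Protocol 6.1 describes permuted block randomization and names no stratification factor. The control-based imputation in SAP 8.8 uses no baseline information for this endpoint either: "For the co-primary endpoint ADCS-CGIC score, the variables for the imputation model will include ADCS-CGIC score at Week 6 and Week 12".

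**The concern.** Neither the randomization nor the model takes account of baseline severity for ADCS-CGIC, and no reason is given. If severity at entry predicts the Week 12 rating, leaving it out keeps explainable variance in the error term. The confidence interval is then wider than it need be, and the estimate moves with whatever chance imbalance in severity occurs. These are two views of the same variance, not two separate losses.

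Precision on this endpoint matters because both co-primaries must be significant at the 5% level before the secondary endpoints can be tested formally (SAP 8.2.1).

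**Working it through.** **Inputs.** Evaluable participants: 210 pooled active, 70 placebo. Two-sided alpha 0.05. ADCS-CGIC SD 0.5 (Protocol 6.2 and 6.10.1, SAP 6). The assumed difference is 0.23 in Protocol 6.2 and SAP 6, but Protocol 6.10.1 has "assuming a delta of 0.22 with a common standard deviation of 0.5". ADAS-Cog11: difference 2.7, SD 6.0. The correlation r is not in the documents, so 0 to 0.4 is an assumed range.

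**Method.** Noncentral t test on 278 df for the Week 12 comparison alone, ignoring what the MMRM borrows from Week 6. The standard error is SD × √(1/210 + 1/70) = SD × 0.1380.

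**The plan's own figures.**
- ADAS-Cog11: 2.7 / (6.0 × 0.1380) = 3.26, power 90.1%. This reproduces the stated 90%.
- ADCS-CGIC at 0.22: 0.22 / (0.5 × 0.1380) = 3.19, power 88.8%. This reproduces the stated 89%.
- ADCS-CGIC at 0.23: power 91.3%, not 89%. The two differences need reconciling as a separate matter. Here it means that ADCS-CGIC is the weaker co-primary at 0.22 but not at 0.23.

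**With the covariate.** The residual SD is 0.5 × √(1 − r²), the equivalent unadjusted sample size is 280 / (1 − r²), and the 95% CI half-width is 1.969 × residual SD × 0.1380.

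| r | Residual SD | Power at 0.22 | Power at 0.23 | Reduction in SE | CI half-width | Equivalent N |
|---|---|---|---|---|---|---|
| 0 | 0.500 | 88.8% | 91.3% | 0 | 0.136 | 280 |
| 0.1 | 0.497 | 89.1% | 91.6% | 0.5% | 0.135 | 283 |
| 0.2 | 0.490 | 90.0% | 92.4% | 2.0% | 0.133 | 292 |
| 0.3 | 0.477 | 91.5% | 93.6% | 4.6% | 0.130 | 308 |
| 0.4 | 0.458 | 93.4% | 95.2% | 8.3% | 0.125 | 333 |

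**Chance imbalance.** The difference between arms in mean baseline severity has standard error 0.138 SD, so its median absolute value is 0.674 × 0.138 = 0.093 SD. The resulting shift in the unadjusted estimate, in either direction, is 0.093 × r × 0.5 = 0.005, 0.009, 0.014 or 0.019 points at r = 0.1 to 0.4. That is about 2, 4, 6 or 8% of 0.22.

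**Cost if the covariate is useless.** At r = 0 and a difference of 0.22, two fewer degrees of freedom lower power from 88.822% to 88.820%.

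**Validity.** A simulation with no true effect (80 vs 240 participants, one visit, 4,000 runs per scenario, r = 0.3 and 0.5) gave these results:
- Dropout at random, or related to baseline equally in both arms: the unadjusted estimate had bias of about 0.001 at most and type I error of 4.3 to 5.6%.
- A stress case, about 12% missing overall, with dropout tied to worse baseline in the active arms only: the unadjusted bias was −0.016 (r = 0.3) or −0.028 (r = 0.5), favouring active, with type I error 5.5% or 6.7%. Adjustment brought the bias below 0.001 and type I error to about 5%.

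The documents neither state nor exclude the stress case.

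**The case against.** The plan contains no error here: Protocol and SAP agree, and the unadjusted test is legitimate. The comparison with the other endpoints is also not like for like. They are adjusted for their own baseline, whereas ADCS-CGIC is already a rating of change and has none. That explains why the ADAS-Cog11 model could not simply be copied. It does not explain leaving out a severity measure that is already scheduled, since a covariate need not be on the outcome's scale.

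The benefit rests on an r that nobody has documented. ADCS-CGIC rates change rather than level, over only 12 weeks, in participants restricted to MMSE 14–24, so a small r is quite possible. This stands: at r = 0.1 the gain is 0.3 points. It also stands that success needs both co-primaries, so the gain in joint power is a little smaller than the table suggests. With ADAS-Cog11 at 90.1%, a difference of 0.22 and an assumed correlation of 0 to 0.5 between the test statistics, joint power rises by about 0.2–0.3, 0.9–1.1, 2.0–2.4 and 3.5–4.1 points at r = 0.1 to 0.4.

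The most serious objection is timing. The sample size re-estimation is done (SAP 8.9). It used conditional power for this endpoint and relies on the conventional final statistic (Protocol 6.10.1), and the decision conveyed to the sponsor carries some information about the results. A late change to a co-primary model therefore has a cost in credibility. Protocol 6.10.2 keeps the sponsor's study team blinded to the interim results, so a documented amendment before unblinding, with the unadjusted analysis retained, is defensible. After unblinding it would not be.

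Finally, the baseline-by-visit interaction proposed below goes beyond the ADAS-Cog11 model, which has a baseline main effect only. It lets the relation to severity differ between Weeks 6 and 12 and is included in the two degrees of freedom costed above.

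**Conclusion.** The point holds as a minor matter of efficiency. Depending on r, adjustment would add between nothing and 4.6 points of ADCS-CGIC power at a difference of 0.22 (3.9 points at 0.23) over r = 0 to 0.4, at a statistical cost below 0.01 points. The gain is modest unless baseline severity predicts the rating fairly well.

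The result rests on the assumed range for r, the planned SD of 0.5, 280 evaluable participants, and a single-visit approximation to the MMRM. The unadjusted analysis is valid under randomization. The one qualification is that the MMRM assumes data missing at random given the terms in the model, so dropout related to severity differently by arm could add a small bias that adjustment would remove.

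**What to change.** Amend the SAP before unblinding:

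1. In 8.2.3, 8.2.7 and 8.6, add baseline ADAS-Cog11 and its interaction with visit to the ADCS-CGIC MMRM.
2. In 8.8, add baseline ADAS-Cog11 to the ADCS-CGIC imputation model, because the primary MMRM is refitted to the imputed data.
3. State how a missing baseline ADAS-Cog11 is handled, for example with the mean over all arms combined, so that nobody with ADCS-CGIC data is dropped. The primary set is all randomized participants, and even the mITT only requires participants to "have both a baseline and at least one postbaseline assessment value for the ADAS-Cog11 or ADCS-CGIC score after taking study drug".
4. Keep the unadjusted model as a sensitivity analysis.
5. SAP 8.1 now reads "There have been no changes in the planned analyses in the study protocol". Record there that this departs from Protocol 6.8 and was made after the sample size re-estimation but blind to treatment results.

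The cost is an amendment to five SAP sections and one or two degrees of freedom. No new data are needed.

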8.2.8 Secondary Analysis

Secondary efficacy endpoints in this clinical trial are

- Change from baseline to Week 12 in ADCS-ADL
- Change from baseline to Week 12 in MMSE score
- Change from baseline to Week 12 in DSST

Change from Baseline to Week 12 in ADCS-ADL

The ADCS-ADL is a 23-item inventory developed as a rater-administered questionnaire answered by the participant's study partner. The ADCS-ADL measures both basic and instrumental activities (instrumental activity items 6a, 7-23) of daily living by participants with a lower score indicating greater severity.

ADCS-ADL score will be analyzed by MMRM, similar to the co-primary endpoint ADAS-Cog11 score.

Change from Baseline to Week 12 in MMSE Score

MMSE is a brief screening instrument used to assess cognitive function (orientation, memory, attention, ability to name objects, follow verbal/written commands, write a sentence, and copy figures). Total score ranges from 0 to 30 with a lower score indicating greater disease severity.

MMSE score will be analyzed by MMRM, similar to the co-primary endpoint ADAS-Cog11 score.

Change from baseline to Week 12 in DSST

In the DSST individuals are asked to record associations between different symbols and numbers within time limits. The total score is the sum of all the correctly coded numbers and higher scores indicate better performance.

DSST score will be analyzed by MMRM, similar to the co-primary endpoint ADAS-Cog11 score.

As the study is also designed to explore the effectiveness of three buntanetap-treatment dose levels on secondary endpoints, similar MMRM will be applied comparing each buntanetap-treatment dose arm with placebo.

